7.1.3. Relationship of Adverse Events to Study Drug

Related AEs are those for which the investigator answers “Yes” to the question “Related to Study Treatment?” in the eCRF. Events for which the investigator did not record relationship to study drug will be considered related to study drug for summary purpose. Data listings will show relationship as missing.

7.1.4. Relationship of AEs to Study Procedure

AEs for which ‘Yes’ is marked for question ‘Related to Study Procedures?’ in the eCRF will be identified and included in AE listing.

7.1.5. Serious Adverse Events

Serious adverse events (SAEs) are those identified as serious in the eCRF, where ‘Yes’ was marked for ‘AE serious’. Serious adverse events captured and stored in the clinical database will be reconciled with the SAE database from the Gilead Global Patient Safety Department before data finalization.

7.1.6. Treatment-Emergent Adverse Events

7.1.6.1. Definition of Treatment-Emergent Adverse Events

Summaries of treatment-emergent AEs will be provided for randomized CCI [REDACTED]

Treatment-emergent AEs occurring during the randomized phase are defined as:

- Any AE with onset date on or after the randomized study drug start date and no later than the minimum of the randomized study drug stop date + 3 days CCI [REDACTED], for those who discontinued randomized study drug permanently, or
- Any AE with onset date on or after the randomized study drug start date for those who are still on the randomized study drug, or
- Any AE leading to randomized study drug discontinuation.

CCI [REDACTED]

- [REDACTED]
- [REDACTED]
- [REDACTED]

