### **8.6.4. Adverse Events**

Clinical and laboratory adverse events will be coded using the Medical Dictionary for Regulatory Activities (MedDRA). System Organ Class (SOC), High-Level Group Term (HLGT), High-Level Term (HLT), Preferred Term (PT), and Lower-Level Term (LLT) will be attached to the clinical database.

Events will be summarized on the basis of the date of onset for the event. A treatment-emergent adverse event will be defined as any adverse event that begins on or after the date of first dose of treatment up to the date of last dose of treatment. Continuing adverse events diagnosed prior to the start of treatment and worsening in severity grade, or non-serious adverse events at baseline which become serious, or adverse events resulting in treatment discontinuation after the start of treatment will also be considered treatment-emergent.

Summaries (number and percentage of subjects) of treatment-emergent adverse events (by SOC, and PT) will be provided by treatment group.

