7.9. Changes From Protocol-Specified Safety Analyses

Treatment-emergent AE and lab abnormality in randomized phase was defined as any AE or lab abnormality that begins on or after the first dose date of study drug up to the last dose date in the protocol, and is updated in this SAP. Treatment-emergent AE occurring in the randomized phase is defined as any AE with onset date on or after the first dose date of the randomized study and no later than the minimum of the randomized study drug stop date + 3 days CCI [REDACTED], if applicable for the randomized phase. Treatment-emergent laboratory abnormalities occurring in the randomized phase are defined as values that increase by at least 1 toxicity grade from baseline at any postbaseline visit up to and including the minimum of the randomized study drug stop date + 3 days CCI [REDACTED] for the randomized phase. This change was made as labs performed 1-2 days after study drug stopped were being excluded causing the measurement for the timepoint to be missed, even though protocol specified visit windows allowed for labs to be performed in a short period after the study drug was stopped.

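### SAP 7.1.6.1 leaves out two of the protocol's four routes to treatment-emergent status (worsened and newly serious pre-treatment AEs), and SAP 7.9 does not declare it

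*SAP*

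**What the plan says.** Protocol 8.6.4 starts from a time window, "any adverse event that begins on or after the date of first dose of treatment up to the date of last dose of treatment". It then widens the definition: "Continuing adverse events diagnosed prior to the start of treatment and worsening in severity grade, or non-serious adverse events at baseline which become serious" also count, and "adverse events resulting in treatment discontinuation after the start of treatment will also be considered treatment-emergent".

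SAP 7.1.6.1 gives three criteria for the randomized phase, joined by *or*:

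- for subjects who stopped drug permanently, "Any AE with onset date on or after the randomized study drug start date and no later than the minimum of" the stop date plus 3 days and a redacted limit;
- "Any AE with onset date on or after the randomized study drug start date for those who are still on the randomized study drug";
- any AE that led to discontinuation of randomized drug.

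SAP 7.1.6.2, on incomplete dates, uses only onset and end dates.

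SAP 7.9 is the section for departures from the protocol's safety analyses. It reports the protocol rule this way: "Treatment-emergent AE and lab abnormality in randomized phase was defined as any AE or lab abnormality that begins on or after the first dose date". The window it describes closes with the last dose. The change it declares is the added 3 days. The reason it gives concerns laboratory samples taken a day or two after stopping.

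**The concern.** Two categories in the protocol's definition have no counterpart in the SAP, and the section meant to disclose such changes does not mention them. A reader of SAP 7.9 would conclude that only the length of the window had changed.

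The treatment-emergent label decides what is tabulated. Every item in the brief AE summary in SAP 7.1.7, and every AE table by system organ class and preferred term, is restricted to treatment-emergent events. Safety and tolerability is part of a primary objective, and the arms are small, so single events are visible in the percentages. An AE that began before Day 1 and worsened or became serious on TAF or TDF could be missing from the by-arm comparison that readers rely on.

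**Working it through.** No figure in the plan needs reproducing. The check is a clause-by-clause comparison, then a trace of which records could be affected.

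**Step 1: the definitions side by side**

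| Route to treatment-emergent | Protocol 8.6.4 | SAP 7.1.6.1 | Protocol rule as described in SAP 7.9 |
|---|---|---|---|
| Onset within the dosing window | yes | yes, extended by 3 days | yes |
| Continuing pre-treatment AE that worsens in grade | yes | no | not mentioned |
| Non-serious baseline AE that becomes serious | yes | no | not mentioned |
| AE resulting in discontinuation | yes | yes | not mentioned |

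The protocol has 4 routes. The SAP keeps 2 and omits 2. SAP 7.9 describes 1 of the 4 and declares neither omission. The same sentence in 7.9 also describes the laboratory rule as abnormalities that begin after first dose, whereas Protocol 8.6.5 uses a grade increase from baseline. That slip has no effect on the analysis, because SAP 7.2.2.1 keeps the grade-increase rule.

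**Step 2: could redaction hide the missing routes?** Probably not. The visible randomized-phase list is closed and ends with a full stop. The redacted block comes after it, and its three bullets look like a parallel list for another phase. This is an inference. The description in 7.9 of the protocol rule is not redacted.

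**Step 3: which records are exposed?**

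- Conditions that predate consent are medical history, not AEs (Protocol 7.1.1). If they worsen during the study, the worsening is itself an AE. Dated at the worsening, it meets the SAP's onset rule and nothing is lost. Dated at the original onset, it is missed. Neither document says which date to use.
- Between consent and first dose, only SAEs and AEs related to protocol procedures are recorded as AEs. Other occurrences go to medical history (Protocol 6.2.1 and 7.3). Screening lasts at most 45 days.
- The worsening route therefore applies mainly to screening-period SAEs and procedure-related AEs that continue past Day 1. The becomes-serious route applies, among these, to non-serious procedure-related AEs only.
- AEs that led to discontinuation count whatever their onset, and treatment-emergent death is defined by date of death, so neither is affected.

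**Step 4: size per event.** Input: about 25 subjects per arm (SAP 1.2). SAP 7.1.7 counts each subject once per summary. If the omitted event is the subject's only qualifying event for that table, the change in incidence is 1/25 = 0.04, or about 4 percentage points. If the subject already has another qualifying event, the change is 0.

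**The case against.** The strongest reply is that the gap is almost entirely on paper. A reader might infer that, because every subject has chronic kidney disease and a transplant and entered on TDF, the commonest harm in this trial, worsening of existing disease, would drop out of the safety tables. The documents do not support that. Baseline kidney and transplant conditions are medical history, and their worsening on study becomes an AE in its own right. Renal and bone worsening is also analysed without reference to AE onset: graded laboratory increases (SAP 7.2.2), confirmed renal abnormalities (7.4.1), eGFR change, percentage decline and CKD stage shifts (7.4.3), Cr EDTA (7.4.8), and BMD change and status shifts (7.3.1). Change in eGFR at Week 24 is the primary safety endpoint.

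Affected events are not lost altogether. The listings of all AEs, Grade 3 and 4 AEs and SAEs in SAP 7.1.7 are not restricted to treatment-emergent events, and SAEs are reconciled with the safety database (7.1.5).

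A reader might also infer that SAP 7.9 misquotes the protocol. It does not quote it. It gives the core sentence in paraphrase and leaves out the extensions.

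All of this stands and limits the consequence. It does not remove the mismatch: the SAP's rule is narrower than the protocol's, the departure is undeclared, and a listing is not a by-arm count. With no stated onset-date convention, the loss cannot be shown to be zero.

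**Conclusion.** The point holds as an undeclared narrowing of a protocol safety definition, with a small expected numerical effect. The events clearly exposed are screening-period SAEs and procedure-related AEs that worsen, or if non-serious become serious, on treatment without causing discontinuation. Worsened pre-existing conditions join them only if sites keep the original onset date. Each such event would be listed but left out of the by-arm TEAE, Grade 3-4 and SAE tables for which it would otherwise qualify. It moves an arm's incidence by about 4 percentage points only if it is that subject's sole qualifying event. The documents give no basis for estimating how many such events there will be.

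This rests on two assumptions: that the redacted text does not restore the missing routes, and that the protocol supplied is the version on which the SAP says it is based (Amendment 3.0), which cannot be confirmed because its title page was removed.

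The change is worth making because a stated rule departs from the protocol without disclosure and the correction is cheap, not because a large distortion is expected.

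**What to change.** 1. Add a fourth criterion to SAP 7.1.6.1: an AE with onset before the randomized study drug start date is treatment-emergent if, on or after that date and inside the treatment-emergent window, it increases in severity grade or changes from non-serious to serious.
2. Align the incomplete-date rules in SAP 7.1.6.2 with this criterion.
3. State which onset date a worsened pre-existing event carries in the eCRF.
4. In SAP 7.9, set out the protocol definition in full, including the grade-increase rule for laboratory abnormalities. If the sponsor means to drop the two routes, say so there and give the reason.
5. If the SAP is already final, record the change in the clinical study report, as SAP Section 1 requires for later changes.

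The cost is one bullet, a corrected paragraph and one flag in the AE dataset. This assumes that the eCRF dates the worsening or the change in seriousness. If it does not, the few AE records with onset before Day 1 that continue on treatment would need a site query.

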7.1.6.2. Incomplete Dates

If an AE onset date is incomplete or completely missing, the following rules will be used to define treatment-emergent AE during the randomized phase CCI [REDACTED]:

Events with Missing Onset Day and/or Month

The event is treatment-emergent during the randomized phase if the following criteria are met:

- The month and year (or year) of onset date is the same as or after the month and year (or year) of the first dose of the randomized study drug, and

- For those who discontinued the randomized study drug permanently only: the month and year (or year) of onset date is the same as or before the month and year (or year) of the minimum of the randomized study drug stop date + 3 days **CCI** and
- AE End date is as follows:
 - The (complete) end date is on or after the first dose date of the randomized study drug, or
 - The month and year (or year) of end date is the same or after the month and year (or year) of the first dose of randomized study drug, or
 - End date is completely missing

CCI

█ [REDACTED]

█ [REDACTED]

█ [REDACTED]

█ [REDACTED]

█ [REDACTED]

█ [REDACTED]

█ [REDACTED]

█ [REDACTED]

Events with Completely Missing Onset Date

An AE with a completely missing onset date is defined as treatment-emergent AE during the randomized phase if end date is as follows:

- The (complete) end date is on or after the first dose date of the randomized study drug, or
- The month and year (or year) of end date is the same or after the month and year (or year) of the first dose of the randomized study drug, or
- End date is completely missing

CCI [REDACTED]

[REDACTED]

[REDACTED]

[REDACTED]

7.1.7. Summaries of Adverse Events and Deaths

A brief summary of AEs (ie, the number and percentage of subjects) will be presented by treatment group for the following: (1) any treatment-emergent AE, (2) any Grade 3 or 4 treatment-emergent AE, (3) any Grade 2, 3 or 4 treatment-emergent AE, (4) any treatment-emergent study drug-related AE, (5) any Grade 3 or 4 treatment-emergent study drug-related AE, (6) any Grade 2, 3 or 4 treatment-emergent study drug-related AE, (7) any treatment-emergent SAE, (8) any treatment-emergent study drug-related SAE, (9) any treatment-emergent AE leading to premature study drug discontinuation, (10) any treatment-emergent AE leading to dose modification or study drug interruption, and (11) any treatment-emergent death.

Treatment-emergent death during the randomized phase refers to death that occurs between the first dose date of the randomized study drug and the minimum of the last dose date of the randomized study drug + 3 days CCI [REDACTED] for those who discontinued randomized study drug permanently. CCI [REDACTED]

Summaries (number and percentage of subjects) of AEs (by SOC, HLT [if specified below], and PT) will be provided by treatment group and overall using the Safety Analysis Set for the randomized phase CCI [REDACTED] as follows:

- All treatment-emergent AEs summarized by SOC, HLT, and PT
- Any Grade 3 or 4 treatment-emergent AEs
- Any Grade 2, 3, or 4 treatment-emergent AEs
- All treatment-emergent study drug-related AE summarized by SOC, HLT, and PT
- Any Grade 3 or 4 treatment-emergent study drug-related AEs
- Any Grade 2, 3, or 4 treatment-emergent study drug-related AEs
- All treatment-emergent SAEs

- All treatment-emergent study drug-related SAEs
- All treatment-emergent AEs leading to premature discontinuation from study drug
- All treatment-emergent AEs leading to dose modification or study drug interruption

Multiple events will be counted once only per subject in each summary. For data presentation, SOC (and HLT) will be ordered alphabetically, with PT sorted by decreasing total frequency. For summaries by severity grade, the most severe event will be selected.

In addition to the by-treatment summaries, data listings will be provided for the following:

- All AEs
- Grade 3 and 4 AEs
- SAEs
- Study drug-related SAEs
- Deaths
- AEs leading to premature discontinuation of study drug
- AEs leading to dose modification or study drug interruption

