## 6.6. Criteria for Discontinuation of Study Treatment

Study medication may be discontinued in the following instances:

- Intercurrent illness that would, in the judgment of the investigator, affect assessments of clinical status to a significant degree. Following resolution of intercurrent illness, the subject may resume study dosing at the discretion of the investigator.
- Unacceptable toxicity, as defined in the toxicity management section of the protocol, or toxicity that, in the judgment of the investigator, compromises the ability to continue study-specific procedures or is considered to not be in the subject's best interest
- Subjects with confirmed  $eGFR_{CKD-EPI}$  of  $< 15 \text{ mL/min/1.73m}^2$  at any time during the study will have their study drug permanently discontinued
- Lack of efficacy (virologic failure)
- HBsAg loss with seroconversion to anti-HBs. These subjects should discontinue study drug within 3-6 months following confirmation of seroconversion to anti-HBs. Subjects with HBsAg loss with confirmed seroconversion before Week 48 are not permitted to discontinue study drug prior to the Week 48 visit
- Discontinuation of study drug for subjects experiencing HBsAg-loss with confirmed seroconversion to anti-HBs, who have known bridging fibrosis or cirrhosis, should be considered on a case by case basis
- Subject request to discontinue for any reason
- Subject noncompliance
- Pregnancy during the study; refer to [Appendix 6](#)
- Discontinuation of the study at the request of Gilead, a regulatory agency or an institutional review board or independent ethics committee (IRB/IEC)

CCI

CCI

CCI

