### **7.1.3. Clinical Laboratory Abnormalities and Other Abnormal Assessments as Adverse Events or Serious Adverse Events**

Laboratory abnormalities are usually not recorded as AEs or SAEs. However, laboratory abnormalities (e.g., clinical chemistry, hematology, urinalysis) independent of the underlying medical condition that require medical or surgical intervention or lead to investigational medicinal product interruption or discontinuation must be recorded as an AE, as well as an SAE, if applicable. In addition, laboratory or other abnormal assessments (e.g., electrocardiogram, X-rays, vital signs) that are associated with signs and/or symptoms must be recorded as an AE or SAE if they meet the definition of an AE (or SAE) as described in Sections 7.1.1 and 7.1.2. If the laboratory abnormality is part of a syndrome, record the syndrome or diagnosis (i.e., anemia) not the laboratory result (i.e., decreased hemoglobin).

Severity should be recorded and graded according to the GSI Grading Scale for Severity of Adverse Events and Laboratory Abnormalities ([Appendix 5](#)). For adverse events associated with laboratory abnormalities, the event should be graded on the basis of the clinical severity in the context of the underlying conditions; this may or may not be in agreement with the grading of the laboratory abnormality.

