### **7.5.2. Grade 3 Laboratory Abnormality or Clinical Event**

- For Grade 3 clinically significant laboratory abnormality or clinical event, investigational medicinal product may be continued if the event is considered to be unrelated to investigational medicinal product.
- For a Grade 3 clinical event, or clinically significant laboratory abnormality confirmed by repeat testing, that is considered to be related to investigational medicinal product, investigational medicinal product should be withheld until the toxicity returns to  $\leq$  Grade 2.
- If a laboratory abnormality recurs to  $\geq$  Grade 3 following rechallenge with investigational medicinal product and is considered related to investigational medicinal product, then investigational medicinal product should be permanently discontinued and the subject managed according to local practice. Recurrence of laboratory abnormalities considered unrelated to investigational medicinal product may not require permanent discontinuation.

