#### 7.5.5.1. For subjects on TDF:

- For subjects with baseline eGFRCKD-EPI  $\geq 50$  mL/min/1.73m^2 that decline to  $< 50$  mL/min/1.73m^2 at any post-baseline visit:
  - If the eGFRCKD-EPI is confirmed to be  $\geq 30$  mL/min/1.73m^2 and  $< 50$  mL/min/1.73m^2, the subject will be required to undergo dose modification to every other day dosing of TDF
  - If the eGFRCKD-EPI is confirmed to be  $\geq 30$  mL/min/1.73m^2 and  $< 50$  mL/min/1.73m^2, and the subject has undergone dose modification to every other day dosing of TDF and subsequently develops a confirmed eGFRCKD-EPI  $\geq 50$  mL/min/1.73m^2, the subject may revert to once daily dosing of TDF after discussion with the Gilead Medical Monitor
- For all subjects with a post-baseline eGFRCKD-EPI  $< 30$  mL/min/1.73 m^2 and  $\geq 15$  mL/min/1.73 m^2:
  - If the eGFRCKD-EPI is confirmed to be  $< 30$  mL/min/1.73m^2 and  $\geq 15$  mL/min/1.73 m^2, the subject will be required to undergo dose modification to every 96 hours dosing of TDF
  - If the eGFRCKD-EPI is confirmed to be  $< 30$  mL/min/1.73 m^2 and  $\geq 15$  mL/min/1.73 m^2, and the subject has undergone dose modification to once every 96 hours dosing of TDF and subsequently develops a confirmed CLCr  $\geq 30$  mL/min/1.73 m^2, the subject may revert to every other day dosing of study drug after discussion with the Gilead Medical Monitor
- For all subjects with a post-baseline eGFRCKD-EPI  $< 15$  mL/min/1.73 m^2:
  - If the eGFRCKD-EPI is confirmed to be  $< 15$  mL/min/1.73 m^2, the subject will be required to permanently discontinue treatment according to Section 7.5.5.3

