#### 7.5.5.2. For subjects on TAF:

- If the eGFRCKD-EPI is confirmed to be  $\geq 15$  mL/min/1.73 m^2, no dose modifications are required

7.5.5.3. For subjects on TAF or TDF:

- All subjects with a confirmed  $eGFR_{CKD-EPI} < 15 \text{ mL/min/1.73 m}^2$  will be required to permanently discontinue treatment
- All subjects with a change from baseline serum creatinine of  $\geq 0.4 \text{ mg/dL}$  must have serum creatinine repeated, with a concurrent urinalysis and urine chemistry, within two weeks of receipt of results

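### The by-arm row in SAP 7.1.7 for AEs that changed or interrupted dosing is not like-for-like: a confirmed eGFR fall to 15 to <50 can compel a dosing change only in the TDF arm

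*SAP*

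**What the plan says.** SAP 7.1.7 lists eleven items for the brief AE summary by treatment group. Item (10) is "any treatment-emergent AE leading to dose modification or study drug interruption". The same category has its own table by system organ class and preferred term ("All treatment-emergent AEs leading to dose modification or study drug interruption") and a listing.

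The protocol's renal rules differ by arm. For TDF (7.5.5.1), when baseline eGFR was at least 50 and a value of 30 to <50 is confirmed, "the subject will be required to undergo dose modification to every other day dosing of TDF". When a post-baseline value of 15 to <30 is confirmed, whatever the baseline, "the subject will be required to undergo dose modification to every 96 hours dosing of TDF". For TAF (7.5.5.2), at any confirmed value of 15 or more, "no dose modifications are required". Below 15 the rule is common to both arms: subjects with such a confirmed value "at any time during the study will have their study drug permanently discontinued" (6.6, repeated in 7.5.5.3).

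Two general provisions also apply to both arms. Under 7.5.2, for a Grade 3 clinical event, or a confirmed and clinically significant Grade 3 laboratory abnormality, judged related to treatment, "investigational medicinal product should be withheld until the toxicity returns to" Grade 2 or lower. Under 7.1.3, laboratory abnormalities are not normally AEs, but those that need intervention or "lead to investigational medicinal product interruption or discontinuation must be recorded as an AE".

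**The concern.** Item (10) reads as a tolerability comparison: how often did an adverse event force a change in treatment? For renal events that depends partly on which arm the subject is in. Suppose a TDF subject and a TAF subject have the same fall in eGFR and the site records the same renal AE for both. The TDF subject must change dosing interval, so the AE led to a dose modification and is counted. The TAF subject may simply continue, and the AE is then not counted in this row.

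Part of any TDF excess could therefore reflect the dosing rules and not tolerability. This matters because the trial compares the renal safety of the two drugs, is open-label, and reports safety descriptively, so readers will compare the raw rows.

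**Working it through.** The plan gives no rate or sample-size figure for this row, so there is nothing to reproduce. The check sets the rules side by side and then asks which routes put a TAF subject in the row.

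**Step 1. What each confirmed post-baseline eGFR compels** (mL/min/1.73 m²; protocol 6.6 and 7.5.5.1 to 7.5.5.3)

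| Confirmed eGFR | TDF arm | TAF arm | Same rule? |
|---|---|---|---|
| 50 or more | No mandated interval change | None | Yes |
| 30 to <50, baseline 50 or more | Mandated interval change | None | **No** |
| 30 to <50, baseline below 50 | No mandated interval change stated | None | Yes |
| 15 to <30, any baseline | Mandated interval change | None | **No** |
| Below 15 | Permanent discontinuation | Permanent discontinuation | Yes, and this belongs to item (9) |

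The asymmetry is confined to the second and fourth rows.

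**Step 2. Can a TAF subject enter item (10) with a renal AE at 15 or above?** Yes, because the item includes interruptions. Protocol Appendix 5 puts Grade 3 creatinine at above 3.00 and up to 6.00 mg/dL. The SAP 7.4.3 CKD-EPI creatinine formula, for creatinine above κ and without the race multiplier, is

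eGFR = 141 × (SCr/κ)^−1.209 × 0.993^age (× 1.018 if female), with κ = 0.9 for men and 0.7 for women.

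At SCr = 3.00:

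- Man aged 60: 141 × (3.00/0.9)^−1.209 × 0.993^60 = 21.6
- Woman aged 60: 141 × (3.00/0.7)^−1.209 × 0.993^60 × 1.018 = 16.2
- Ages 40 to 70: 24.8 down to 20.1 in men, 18.7 down to 15.1 in women

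Grade 3 creatinine can therefore occur above 15, in the lower part of the 15 to <30 band. If it is judged related and clinically significant, TAF is withheld and any AE recorded for it enters item (10).

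**Step 3. The 30 to <50 band.** Solving the same formula for creatinine at ages 40 to 70 gives 1.12 to 1.68 mg/dL at eGFR 50 and 1.70 to 2.57 mg/dL at eGFR 30. All are below 3.00, so creatinine alone does not reach Grade 3 here. Protocol 7.5.1 leaves continuation through Grade 1 and 2 to the investigator. A TAF entry then needs a discretionary interruption or a related Grade 3 clinical event. A TDF subject with baseline of at least 50 must change interval.

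**Step 4. Does the SAP correct for this?** Section 7.1.7 has no split and no footnote. Section 7.9 covers only the treatment-emergent window. Section 7.4.1 does tabulate confirmed falls from at least 50 to below 50, and confirmed values below 30, with the same definitions in both arms.

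**Step 5. Scale.** One subject is 1/25 = 4% of an arm. If a share p of TDF subjects met the rule and also had an AE recorded for it, the row would gain 25p subjects: 0 at p = 0, 1.25 at 5%, 2.5 at 10%, 5 at 20%. These values of p are assumptions; the documents support none over another.

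**The case against.** The strongest reply is that the row counts AEs, not dose changes. Protocol 7.1.3 makes a laboratory abnormality an AE when it needs intervention or leads to interruption or discontinuation. It does not name dose modification, and it limits the exception to abnormalities independent of the underlying condition, in a trial where every subject enrols with chronic kidney disease. A site could change a TDF interval and record no AE. This stands, and it is why no size can be given. It does not remove the asymmetry: 7.1.1 treats worsening of a pre-existing condition as an AE, so a renal AE can be recorded in either arm, and once recorded its route into item (10) differs by arm.

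A second reply is that the fair comparison is already planned. SAP 7.4.1 uses arm-neutral thresholds, 7.4.3 adds percentage declines and CKD stage shifts, and the preferred-term table and listing make renal entries visible. This also stands and limits the harm. But nothing in 7.1.7 tells a reader of item (10) to look there.

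A reader might infer that a renal event above 15 cannot count against TAF. The documents do not support that: interruptions are included, withholding for related Grade 3 events applies to both arms, and Step 2 shows Grade 3 creatinine is reachable. Nor does every TDF value below 50 trigger a change, since the 30 to <50 rule needs a baseline of at least 50.

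**Conclusion.** The concern holds in a limited form. Item (10) is not like-for-like for renal AEs recorded at the eGFR values in the second and fourth rows of the Step 1 table, and its lean is against TDF.

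The conclusion assumes that sites record at least some renal AEs at these values and attribute the TDF interval change to them. If they never do, the row is unaffected. Simulating eGFR threshold crossings would not supply the missing size: it would count dose changes, not AEs, under assumed baseline values and variability.

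A reader might also infer that the primary renal comparison is biased by this. It is not: the primary safety endpoint is the change in eGFR at Week 24, and item (10) does not feed it. The row is a descriptive summary with no test attached. No view is taken here on the dosing rules themselves.

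**What to change.** In SAP 7.1.7, for item (10) and its table by system organ class and preferred term:

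- Report AEs whose only action was a protocol-mandated TDF interval change under 7.5.5.1 separately from all other dose modifications and interruptions.
- Footnote that no such rule applies to TAF at eGFR of 15 or more.
- Refer readers to SAP 7.4.1 for the between-arm comparison at the 50 and 30 thresholds.

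The mandated changes can be identified from the eGFR results and study drug administration records already held. This assumes those records show the TDF dosing interval; the form itself is not reproduced in the documents. The SAP was signed in June 2021, after the Week 24 and Week 48 analyses, so the split should be labelled as added for the final analysis. New recording instructions to sites would come too late for randomized-phase AEs and are not proposed.

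The cost is one extra row, a footnote and a small classification step. No new data are needed.
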